9.3.8. Adverse Events of Special Interest

AESIs for this study include:

- Any severe hypersensitivity reactions.
- Plantar fascial tears.

These events will be reported as AEs in the eCRF. All AESIs will be evaluated for seriousness and severity. If any of these events meet the criteria for an SAE, they will also be reported as such using the procedure outlined in Section 11.3.

9.3.9. Anaphylaxis

Anaphylaxis is a serious allergic reaction that is rapid in onset and may cause death. To identify participants experiencing such a reaction, use the criteria provided by [Sampson et al \(2006\)](#) in [Table 4](#). Anaphylaxis will be reported as an SAE in the eCRF.

Table 4: Clinical Criteria for Diagnosing Anaphylaxis

Anaphylaxis is highly likely when any 1 of the following 3 criteria are fulfilled:	
1.	Acute onset of an illness (minutes to several hours) with involvement of the skin, mucosal tissue, or both (eg, generalized hives, pruritus or flushing, swollen lips-tongue-uvula) AND AT LEAST ONE OF THE FOLLOWING
a.	Respiratory compromise (eg, dyspnea, wheeze-bronchospasm, stridor, reduced peak expiratory flow, hypoxemia)
b.	Reduced blood pressure or associated symptoms of end-organ dysfunction (eg, hypotonia [collapse], syncope, incontinence)
2.	Two or more of the following that occur rapidly after exposure to collagenase or any other excipient of EN3835 for that participant (minutes to several hours):
a.	Involvement of the skin-mucosal tissue (eg, generalized hives, itch-flush, swollen lips-tongue-uvula)
b.	Respiratory compromise (eg, dyspnea, wheeze-bronchospasm, stridor, reduced peak expiratory flow, hypoxemia)
c.	Reduced blood pressure or associated symptoms (eg, hypotonia [collapse], syncope, incontinence)
d.	Persistent gastrointestinal symptoms (eg, crampy abdominal pain, vomiting)
3.	Reduced blood pressure after exposure to collagenase or any other excipient of EN3835 for that participant (minutes to several hours):
a.	Adults: systolic blood pressure of less than 90 mm Hg or greater than 30% decrease from that person's baseline

9.4. Treatment Overdose

Study intervention overdose is any accidental or intentional use of treatment in an amount higher than the dose indicated by the protocol for that participant. Study intervention compliance should be reviewed to detect potential instances of overdose (intentional or accidental).

Any treatment overdose during the study should be noted on the study intervention eCRF.

An overdose is not an AE per se, however all AEs associated with an overdose should both be entered on the AE eCRF and reported using the procedures detailed in Section 11.3, even if the events do not meet seriousness criteria. If the AE associated with an overdose does not meet seriousness criteria, it must still be reported using the Endo Serious Adverse Event (SAE)/ Reportable Event Form and in an expedited manner, but should be noted as nonserious on the form and the AE eCRF.

9.4.1. Treatment Abuse/Misuse

Not applicable.

9.5. Pharmacodynamics

Not applicable.

9.6. Genetics

Not applicable.

9.7. Biomarkers

Not applicable.

9.8. Immunogenicity Assessments

Serum samples will be collected at the time points listed in the Schedule of Assessments and will be tested for binding anti-AUX-I and anti-AUX-II antibodies. If the participant tests positive for anti-AUX-I and anti-AUX-II antibodies, testing for neutralizing antibodies will be conducted.

The serum samples obtained will be processed, stored, and then shipped frozen on dry ice to Endo's appointed laboratory for the determination of anti-AUX-I and anti-AUX-II antibodies.

Specific instructions for the collection, processing, storage, handling, and shipment of the immunogenicity samples will be provided in the Laboratory Manual.

De-identified immunogenicity samples may be stored for a maximum of 5 years (or according to local regulations) following the last participant last visit for the study at a facility selected by the sponsor. This will enable further analysis of immune responses; develop methods, assays, prognostics, and/or companion diagnostics related to specify the intervention target, disease process, pathways associated with disease state, and/or mechanism of action, of the study intervention.

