 - ^d Any diagnostic, therapeutic, or surgical procedure performed within the past 10 years before the study, including those in the treatment area, should be recorded including the date, indication for, and description of the procedure.
 - ^e For women of childbearing potential.
 - ^f A complete physical examination, including height and weight at Screening.
 - ^g Testing for neutralizing antibodies will be conducted if the participant tests positive for anti-AUX-I and anti-AUX-II antibodies.
 - ^h Vital signs (ie, blood pressure, pulse, respiratory rate, and temperature) should be collected in a seated position after the participant has been sitting for 5 minutes.
 - ⁱ Vital signs should be collected in supine position prior to treatment and at 15 (\pm 5) and 30 (\pm 5) minutes post treatment.
 - ^j Opioid analgesic use is prohibited during the study. Acetaminophen and over-the-counter (OTC) nonsteroidal anti-inflammatory drugs (NSAIDs) are permitted if the investigator deems it necessary.
 - ^k Participants will complete the scale prior to evaluation by the investigator. The order of scale completion by the participant is as follows: FFI, PGIS Foot Pain Subscale, PGIC Foot Pain Subscale, PGIS Difficulty Subscale, PGIC Difficulty Subscale, PGIS Activity Limitation Subscale, PGIC Activity Limitation Subscale, PGIS PF Overall, PGIC PF Overall, Pain Intensity NRS, and Subject Satisfaction with Treatment Scale.
 - ^l Palpation for nodular consistency. For Treatment 1, only hard, firm throughout, moderately firm nodules will be treated. For Treatment 2, palpable nodules that are hard, firm throughout, moderately firm, or soft on clinical examination and measurable by caliper, that were previously treated, will be treated.
 - ^m The investigator will complete a graphic representation of the foot/feet and the location of the nodule(s) that are present.
 - ⁿ Randomized in a 1:1 ratio to either EN3835 or placebo using an Interactive Response Technology (IRT) system.
 - ^o Size of the nodule(s) will be determined by caliper and the largest width or length will be used to determine number of injections to be administered.
 - ^p On Visit Day 29, urine pregnancy testing will only be performed if the participant will receive a second treatment of study intervention.
 - ^q Including concomitant surgical and medical procedures for plantar fibromatosis and for conditions other than plantar fibromatosis.

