
 To assess the safety and tolerability of EN3835 in participants with plantar fibromatosis. 	
 Safety of EN3835 as assessed by incidence, severity and duration of treatment-emergent adverse events (TEAEs), adverse events of special interest (AESIs), and serious adverse events (SAEs). The change from baseline in vital signs and clinical laboratory values at each visit where these parameters are measured.

 To assess the immunogenicity of EN3835 in participants with plantar fibromatosis. 	
 Presence of anti-AUX-I and anti-AUX-II antibody titer levels in EN3835 treated-participants at Day 1 and Day 57. Presence of neutralizing antibodies to AUX-I and AUX-II in EN3835 treated-participants at Day 1 and Day 57.
Exploratory	

 To assess the overall improvement in the FFI composite score with EN3835 vs placebo. 	
 The difference between EN3835 and placebo in the mean change from Baseline (Day 1) to Day 57 on the FFI composite score, with the score of each of the 21 items ranging from 0 to 4, with 4 indicating higher severity. The mean change from Baseline (Day 1) to Days 15, 29, 43, and 57 on the FFI composite score with EN3835 vs placebo.

 To assess the overall improvement in severity of plantar fibromatosis on the Patient Global Impression of Severity (PGIS) PF Overall scale. 	
 The difference between EN3835 and placebo at Day 57 on the PGIS PF Overall score. The difference between EN3835 and placebo Days 15, 29, 43, and 57 on the PGIS PF Overall score with EN3835 vs placebo.

 To assess the overall improvement in the severity of foot pain with EN3835 vs placebo in the PGIS foot pain subscale. 	
 The difference between EN3835 and placebo at Day 57 on the foot pain subscale of the PGIS. The difference between EN3835 and placebo at Days 15, 29, 43, and 57 on the PGIS foot pain subscale, ranging from 0 ("None") to 4 ("Severe") with EN3835 vs placebo.

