10.3.2.3. Immunogenicity Analysis

Anti-AUX-I and anti-AUX-II antibody results (titer levels) and neutralizing antibodies to AUX-I and AUX-II will be summarized using descriptive statistics.

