4.10. Immunogenicity

Serum samples will be collected and will be tested for binding anti-AUX-I and anti-AUX-II antibodies. The subset of the samples will be tested for neutralizing antibodies if the sample results are positive for anti-AUX-I or anti-AUX-II.

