7.7.7. Immunogenicity

7.7.7.1. Presence of anti-AUX-I and anti-AUX-II antibody titer levels

The following will be summarized: the number of participants with an immunogenicity sample collected, the percentage of participants with positive and negative anti-AUX-I and anti-AUX-II antibodies, the titer level of the positive samples at Screening and Day57/EOS.

The titer levels will be logarithmically transformed prior to being summarized. Samples from Screening and Day 57/EOS will be analyzed for anti-AUX-I and anti-AUX-II antibodies.

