7.7.7.2. Presence neutralizing antibodies to AUX-I and AUX-II

A subset of positive samples of AUX-I or AUX-II will be analyzed for neutralizing antibodies. Neutralizing antibody results will be summarized as percentage of positive/negative results by visit and treatment group if applicable.

A listing of immunogenicity results by participant will be provided.

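### The trigger for neutralizing-antibody testing conflicts: positive for anti-AUX-I and anti-AUX-II in four places, positive for either (and only a subset) in two

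*Protocol*

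**What the plan says.** Four places make neutralizing testing conditional on both binding antibodies. Protocol 9.8 reads "If the participant tests positive for anti-AUX-I and anti-AUX-II antibodies, testing for neutralizing antibodies will be conducted". Footnote g of the Schedule of Assessments in Protocol 2.3 reads "Testing for neutralizing antibodies will be conducted if the participant tests positive for anti-AUX-I and anti-AUX-II antibodies". SAP Table 2 footnote g repeats that footnote, and SAP 3.19 repeats Protocol 9.8.

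Two places in the SAP use *or*. SAP 4.10 says "The subset of the samples will be tested for neutralizing antibodies if the sample results are positive for anti-AUX-I or anti-AUX-II". SAP 7.7.7.2 says "A subset of positive samples of AUX-I or AUX-II will be analyzed for neutralizing antibodies".

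The result feeds a safety endpoint in Protocol 4, carried into SAP Table 1: "Presence of neutralizing antibodies to AUX-I and AUX-II in EN3835 treated-participants at Day 1 and Day 57". The analysis is descriptive; under Protocol 10.3.2.3, "neutralizing antibodies to AUX-I and AUX-II will be summarized using descriptive statistics". SAP 7.7.7.2 makes this a percentage positive and negative by visit and, if applicable, by arm.

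On timing, SAP 7.7.7.1 says "Samples from Screening and Day 57/EOS will be analyzed for anti-AUX-I and anti-AUX-II antibodies". The schedules in both documents and SAP 3.19 collect these samples at Day 1 and Day 57, with none at Screening. SAP Table 28, which lists changes from the protocol, contains only the classification of prior medications.

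**The concern.** The SAP contradicts both the protocol and itself on a rule that decides who has data for a listed endpoint. Protocol 3.2 describes AUX-I and AUX-II as not immunologically cross-reactive, so a sample can be positive for one binding antibody and negative for the other. A laboratory that follows Protocol 9.8 to the letter would stop there for such a participant. One that follows SAP 4.10 would go on.

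At stake are the completeness and the denominator of a descriptive safety percentage. If only double-positive participants are tested and the percentage is taken over those with a result, it describes a selected group, and the table would not show this.

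**Working it through.** The plan states no figure on this point, so there is nothing to reproduce. The check is a comparison of the texts, followed by two illustrations on stated assumptions.

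**1. The six statements side by side.**

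| Place | Condition | Unit | Which positives |
|---|---|---|---|
| Protocol 9.8 | and | participant | all |
| Protocol 2.3, footnote g | and | participant | all |
| SAP Table 2, footnote g | and | participant | all |
| SAP 3.19 | and | participant | all |
| SAP 4.10 | or | sample | a subset |
| SAP 7.7.7.2 | or | sample | a subset |

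The connective, the unit and the coverage all change. A participant-level trigger also leaves open whether a positive Day 57 result sends the Day 1 sample for testing.

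**2. Where the rules part.** A double-negative sample is tested under neither rule. A double-positive sample is tested under literal *and*, and under *or* if *subset* means no further selection. Only a single-positive sample is treated differently: untested under literal *and*, tested under *or*.

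**3. Effect on the percentage.** SAP 6.1 gives two general denominators: first the participants in the relevant population, then, for percentages, those with non-missing values. Under the second, the trigger sets the denominator.

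The only antibody counts in the documents are in Protocol 3.2.1: in Study EN3835-105, at Day 57 of the Retreatment Period, 10/10 had neutralizing AUX-I and 8/10 neutralizing AUX-II antibodies. *Assume*, for illustration, that the two without AUX-II neutralizing antibody were also negative for AUX-II binding antibody, and that all ten were positive for AUX-I binding antibody. The documents say neither.

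| Trigger and denominator | AUX-I | AUX-II |
|---|---|---|
| Literal *and*, over those tested | 8/8 = 100% | 8/8 = 100% |
| Each antibody to its own assay, over those tested | 10/10 = 100% | 8/8 = 100% |
| Each antibody to its own assay, over all sampled, binding-negatives counted as negative | 10/10 = 100% | 8/10 = 80% |

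Literal *and* loses two AUX-I results. The choice of denominator alone moves AUX-II from 80% to 100%. Correcting the trigger without stating the denominator would therefore settle only half the matter.

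**4. How many could be missed.** With binding-positive proportions p1 and p2, the single-positive share is at least |p1 − p2| and at most p1 + p2 − 2·max(0, p1 + p2 − 1). The inputs are an EN3835 arm of about 86 (Protocol 5.1), or 0.85 × 86 ≈ 73 after the planned 15% dropout (Protocol 10.1). The rates are assumed.

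| Assumed p1 / p2 | Share | Of 86 | Of 73 |
|---|---|---|---|
| 100% / 100% | 0 | 0 | 0 |
| 100% / 95% | 0.05 | 4.3 | 3.7 |
| 95% / 95% | 0 to 0.10 | 0 to 8.6 | 0 to 7.3 |
| 100% / 80% | 0.20 | 17.2 | 14.6 |

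These rows show only how the loss depends on unknown rates. The last row borrows neutralizing rates as if they were binding rates. None of it estimates this trial, and nothing in the documents gives a rate at Day 1.

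**The case against.** The strongest reply is that this is loose drafting with no consequence. In Protocol 9.8 the sentence before the trigger names both antibodies as a plain list of two assays, and the trigger can be read the same way: each positive result goes on to its own neutralizing assay. SAP 4.10 and 7.7.7.2 fit that reading, and no passage says that single-positive samples are excluded. In SAP 4.10, *the subset* may simply mean the positive samples. The product is an approximately 1:1 mixture of the two enzymes (Protocol 3.2), so exposure is to both, and double positivity may be the rule. Reporting among those tested is also a legitimate summary. EN3835-105 reported no clinically relevant findings in antibody-positive participants, and stored serum may make an omission recoverable.

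Much of this stands. It means that untested single-positives are a consequence of the literal wording, not a certainty. It does not remove the contradiction: a laboratory cannot tell from the text which reading is meant, and SAP 7.7.7.2 is harder than 4.10 to read as meaning all positives.

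A reader might go further and infer that the endpoint itself is wrong. The documents do not support that: its definition is the same in both, and only the testing rule and denominator are unsettled. A reader might also infer that the problem is worst at Day 1. Prior collagenase use is excluded only within 30 days, so some Day 1 positivity is possible, but no passage says how common it is or whether it involves one antibody or both.

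**Conclusion.** The conflict is real and needs correcting; its severity is minor. Six passages give two incompatible triggers, the SAP disagrees with itself as well as with the protocol, and the change is not declared. Under the literal *and* rule, the percentage of neutralizing-antibody positives at Day 1 and Day 57 could be incomplete and taken over a selected group. That conclusion rests on the literal reading and on some participants being positive to one protein only. Without binding-antibody rates the size cannot be given, and it is zero if every positive is a double positive. The endpoint is descriptive, with no hypothesis test, and no primary or key secondary analysis depends on it. The Screening label in SAP 7.7.7.1 is a separate slip that adds no weight to the main point.

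**What to change.** - Use one trigger in Protocol 9.8, Protocol Schedule of Assessments footnote g, SAP Table 2 footnote g, and SAP 3.19, 4.10 and 7.7.7.2. Apply it per sample and per antibody: each sample positive for anti-AUX-I is tested for AUX-I neutralizing antibody, and each sample positive for anti-AUX-II for AUX-II neutralizing antibody. Both footnotes must change, or the SAP will still contradict itself.
- Delete *A subset of* in SAP 7.7.7.2 and *The subset of* in SAP 4.10.
- State the denominator in SAP 7.7.7.2. One option is all participants with a sample at that visit, with results among binding-positives shown alongside. Other conventions are defensible; what matters is that one is named.
- Change Screening to Day 1 in SAP 7.7.7.1.

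The cost is a clarification to the laboratory, the wording changes, and possibly a few extra assays. No new blood draw is needed, and Protocol 9.8 allows storage for up to 5 years after the last participant's last visit, so testing of any missed samples should be feasible.

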10. STATISTICAL CONSIDERATIONS AND METHODS

10.1. Sample Size Determination

The primary endpoint is the difference between EN3835 and placebo in the mean change from Baseline (Day 1) to Day 57 on the foot pain subscale (total score on 9 items) of the FFI ranging from 0 ("None") to 4 ("Extreme").

The sample size was estimated based on an interim analysis of the Day 57 data from Study EN3835-105, a dose-finding Phase 1 study. Assuming a difference in the mean change from Baseline to Day 57 in the pain subscale of FFI between EN3835 and placebo of 5.0 with a 10 standard deviation and 85% statistical power using a 2-sided test ($\alpha = 0.05$), 73 participants per treatment group (146 in total) will be needed to detect this difference between the 2 treatment groups. Assuming a dropout rate of 15%, the total sample size will be 172, eighty-six per treatment group for the study.

Participants will be screened to ensure that approximately 172 participants are randomized into 2 treatment groups, an EN3835 group and a placebo group in a 1:1 ratio.

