10.3.1. Efficacy Analysis

The ITT population will be the primary population for the efficacy analysis. Efficacy analyses will also be performed for the FAS and mITT populations as supportive analyses.

For the data collected at nodule level, the analyses will be performed at participant level and nodule level. The data interpretation will be based on participant level results. The nodule level results will be supportive. The details of how to map the data from nodule level to participant level will be specified in the SAP.

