10.3.1.1. Primary Analysis

10.3.1.1.1. Primary Estimand

Primary Endpoint:

The difference between EN3835 and placebo in the mean change from Baseline (Day 1) to Day 57 on the foot pain subscale (total score on 9 items) of the FFI ranging from 0 (“None”) to 4 (“Extreme”).

The primary estimand is defined as follows:

In participants with plantar fibromatosis, what is the difference in mean change from baseline (Day 1) to Day 57 in foot pain score (as measured with the FFI pain subscale) between EN3835 and placebo regardless of discontinuation of study intervention?

The primary estimand includes the following components:

- Treatment of interest: The randomized study intervention (EN3835 or placebo)
- **Target Population:** Adult participants with plantar fibromatosis who are included in the ITT Population.
- **Variable (Endpoint) of interest:** Change from Baseline (Day 1) to Day 57 in FFI pain subscale score.
- **Treatments being compared:** The mean change from Baseline (Day 1) to Day 57 in FFI pain subscale score will be compared between EN3835 and placebo.
- **Intercurrent Event:** The treatment policy strategy will be adopted for primary analysis.
 - Any new or change in concomitant treatment will not be adjusted for in the primary analysis.
 - Early discontinuation from the study or loss to follow up: If participants do not have a FFI pain subscale score at Day 57, the missing values will be imputed before the analysis using a multiple imputation washout model. In multiple imputation washout model, all participants who are randomized and have a baseline assessment will be considered.
- **Population Level-Summary measure:** Least square mean (LSM) estimates for treatment difference between EN3835 and placebo.

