3.5. Determination of Sample Size

The primary endpoint is the difference between EN3835 and placebo in the mean change from Baseline (Day 1) to Day 57 on the foot pain subscale (total score on 9 items) of the FFI ranging from 0 (“None”) to 4 (“Extreme”).

Assuming a difference in the mean change from Baseline to Day 57 in the pain subscale of FFI between EN3835 and placebo of 5.0 with a 10 standard deviation and 85% statistical power

using a 2-sided test ($\alpha = 0.05$), 73 participants per treatment group (146 in total) will be needed to detect this difference between the 2 treatment groups. Assuming a dropout rate of 15%, the total sample size will be 172, 86 per treatment group for the study.

Participants will be screened to ensure that approximately 172 participants are randomized into 2 treatment groups, an EN3835 group and a placebo group in a 1:1 ratio.

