6.3.1. Handling of Missing Data for the Primary Endpoint

The foot pain subscale score will be recorded at baseline and at each visit (ie, Day 15, 29, 43, and 57).

The primary endpoint will be the change from baseline at Day 57. This value will be missing if the participants have missing data due to discontinuation from the study prior to Day 57 or due to a missed assessment or lost to follow up.

The missing data at Day 57 will be imputed for the participants who withdraw from the study prior to Day 57 using multiple imputation washout model (Section 7.6.1.2) to explore the possibility of data missing not at random (MNAR). In the multiple imputation washout framework, for participants who withdraw from the study early, their missing values will be

imputed under the assumption that their outcome would be similar to those in the placebo group with similar background characteristics. Multiple imputation methods will be used to account for uncertainty in the imputation process and results from the imputed datasets will be combined using Rubin's method.(4)

In addition, to assess the impact of missing values, sensitivity analyses using Mixed Model Repeated Measure (MMRM) (Section 7.6.1.3) without imputation and with imputation using Tipping Point Analyses (Section 7.6.1.2) will be performed on primary endpoint and key secondary endpoints. If the primary analyses of primary endpoint and key secondary endpoints result is not significant ($p\text{-value} > 0.05$), no sensitivity analyses (tipping point) will be performed.

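### The stated 85% power is that of a completers-only comparison; it is not shown for the primary ITT analysis with washout imputation, where it could be about 75–76%

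*Protocol*

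**What the plan says.** Protocol 10.1 assumes a difference "between EN3835 and placebo of 5.0 with a 10 standard deviation and 85% statistical power using a 2-sided test" at alpha 0.05 and concludes that "73 participants per treatment group (146 in total) will be needed to detect this difference between the 2 treatment groups". It then adds: "Assuming a dropout rate of 15%, the total sample size will be 172, eighty-six per treatment group for the study". SAP 3.5 repeats this: "Assuming a dropout rate of 15%, the total sample size will be 172, 86 per treatment group for the study". Neither section adjusts the 5.0 points or the power for how dropouts are analysed.

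The analysis is set out elsewhere. Protocol 10.3.1: "The ITT population will be the primary population for the efficacy analysis". For participants without a Day 57 score after early discontinuation or loss to follow-up, Protocol 10.3.1.1.1 says "the missing values will be imputed before the analysis using a multiple imputation washout model". SAP 6.3.1 gives the assumption: values for early withdrawals are "imputed under the assumption that their outcome would be similar to those in the placebo group with similar background characteristics". SAP 7.6.1.1 fits an ANCOVA to each imputed dataset and pools by Rubin's method. The detailed imputation steps in SAP 7.6.1.2 are redacted in the public version.

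**The concern.** Dividing by 0.85 replaces lost observations. It is the right correction when dropouts leave the analysis and those who remain carry the full effect. Here the dropouts stay in, and those from the EN3835 arm are given an outcome resembling placebo, so the tested difference shrinks. Rubin's variance also adds an imputation component. The sample size section therefore describes one analysis and the plan carries out another.

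At stake is how a non-significant result would be read. The primary test gates all three key secondary tests (Protocol 10.4, SAP 6.5). The plan tells readers that the chance of missing a 5.0-point effect is 15%; on one natural reading of its own text it is about 24–25%.

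**Working it through.** **Inputs.** Difference Δ = 5.0, SD 10, two-sided alpha 0.05, 73 evaluable and 86 randomised per arm, dropout d = 0.15 (Protocol 10.1). Placebo-like imputation (SAP 6.3.1). ANCOVA pooled by Rubin's method (SAP 7.6.1.1).

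**1. The plan's own figure.** A two-sample t test needs 72.8, so 73 per arm, with 85.1% power at 73. Then 73/0.85 = 85.9, so 86 per arm and 172 in total. Both figures reproduce, and 85% is the power with 73 completers per arm.

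**2. Expected ITT difference.** If 15% of the EN3835 arm are imputed like placebo, it is (1 − d)Δ = 0.85 × 5.0 = 4.25.

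**3. Dilution alone.** With 4.25 and SD 10 at 86 per arm, SE = 10√(2/86) = 1.525 and 4.25/1.525 − 1.96 = 0.827. Power is 79.6% by the normal approximation and 79.1% by t test.

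**4. With Rubin's variance, imputing from baseline only.**
- Within-imputation variance: W = (200 + 0.15 × 0.85 × 25)/86 = 2.363.
- Between-imputation variance: 12.9 imputed per arm, B = 2 × 0.15² × 100/12.9 = 0.349. The uncertainty in the placebo regression is common to both arms and cancels.
- Rubin SE = √(2.363 + 0.349) = 1.647.
- Actual sampling SD of the estimate: 0.85 × 10 × √(2/73.1) = 1.406.
- Power = Φ[(4.25 − 1.96 × 1.647)/1.406] = Φ(0.727) = 76.6%.

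Simulation (4,000 trials, 13 of 86 missing per arm, 25 imputations, ANCOVA, Rubin pooling) gave 75.6% and, in a separately coded run, 76.2%.

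The estimate and its sampling SD shrink by the same factor. If the SE were 1.406, power would be 85.6%. The loss therefore depends on using Rubin's variance, which is what the SAP specifies.

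**5. Other readings at 86 per arm.** Except where the row says otherwise, conditions are as in step 4.

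| Reading | Power |
|---|---|
| Covariates explain 10% of the variance (assumed) | about 79–80% |
| Covariates explain 20% (assumed) | about 84–86% |
| Imputed share 10% / 5% / 20% (formula in step 4) | 82.4% / 87.1% / 69.6% |
| Washout using a Day 29 score for every dropout, full effect by Day 29, within-person correlation 0.5 / 0.7 (assumed) | 83.8% / 86.4% |
| MAR imputation | 84.5% |
| 5.0 is the ITT difference, i.e. 5.0/0.85 = 5.88 among completers | 89.1% |

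**6. Effect needed for 85% under step 4.** Simulated power was 83.9% at 5.6 points and 89.1% at 5.88. Linear interpolation gives 5.6 + 0.28 × (85 − 83.9)/(89.1 − 83.9) = 5.66, so about 5.6–5.7 points among completers.

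**The case against.** The strongest reply is that 76% belongs to one branch of several that the documents leave open.

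- **Imputation steps.** The redacted text of SAP 7.6.1.2 may use scores from Days 15, 29 and 43. If most dropouts have such scores, little power is lost. This stands. The reference to background characteristics in SAP 6.3.1 and the Baseline and Day 57 basis in Protocol 10.3.1.1.2 point towards baseline-only imputation but do not prove it.
- **MAR or MNAR.** SAP 7.6.2 describes the 7.6.1.2 analysis as resting on MAR, whereas SAP 6.3.1 presents the washout model as exploring MNAR. Under MAR the stated power is about right. The washout label and the placebo-like assumption favour MNAR, but the conflict is the plan's to resolve.
- **Meaning of 5.0.** Protocol 10.1 and the estimand in 10.3.1.1.1 word the endpoint alike, so 5.0 could be the ITT difference. The cited source does not help: Study EN3835-105 was open-label with three EN3835 concentrations and no placebo arm (Protocol 3.2.1), so it could not supply an observed difference from placebo of either kind.
- **Covariates and imputed share.** The ANCOVA may reduce the residual SD below 10. Participants who stop treatment but attend Day 57 are not imputed (Protocol 8.1), and those lost to follow-up may be replaced (8.3). Both could raise power, but the plan claims neither gain and gives 15% as its dropout rate.

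A reader might also infer that Amendment 04 reduced N because of this omission. The Summary of Changes does not support that. It attributes the cut to moving from 90% to 85% power and from 20% to 15% dropout. The earlier total follows from the same method (86 per arm at 90% power; 172/0.8 = 215, rounded up to 216), so the omission predates the cut.

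**Conclusion.** The concern holds in conditional form. Nothing in Protocol 10.1 is miscalculated, but its 85% belongs to a completers-only comparison and is not shown for the planned primary analysis. Power is about 75–76% with Rubin's variance, or about 79% from dilution alone, under four assumptions: 5.0 is the effect among participants with Day 57 data; 15% per arm lack those data; imputation uses baseline information only; and covariates bring no gain. Relaxing these one at a time gives about 79% to 89%, including values close to 85% under MAR or with post-baseline scores from most dropouts.

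A reader might conclude flatly that the trial has 76% power. The documents do not support that, because the imputation steps are not visible, the SAP describes them in two incompatible ways, and the status of the 5.0 is not stated.

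**What to change.** Keep N = 172. In Protocol 10.1 and SAP 3.5:

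1. State whether 5.0 is the difference among participants with Day 57 data or the ITT difference after imputation.
2. Replace the 85% with the power of the primary analysis under the washout imputation actually specified and Rubin's pooling, naming the share imputed, the scores used and any covariate gain assumed. For a 5.0-point completer effect with baseline-only washout and no covariate gain, the figure is about 75–80%. Roughly 85% or more would need about 5.6–5.7 points among completers, or a 5.0-point ITT effect.
3. Reconcile SAP 7.6.2 (MAR) with SAP 6.3.1 (MNAR), since the power figure depends on which applies.

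The cost is a less favourable stated power. No participants are added, and the primary analysis does not change unless item 3 shows that MAR was intended.
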